#### ***Appendix 3.2.1. Data Capture System***

An electronic data capture system will be used in this study. The site will maintain a separate source for the data entered by the site into the sponsor-provided electronic data capture system. Electronic case report form data will be encoded and stored in a clinical trial database. Data managed by a central vendor will be stored electronically in the central vendor's database system. Data will subsequently be transferred from the central vendor to the Lilly data warehouse.

Any data, for which paper documentation provided by the subject will serve as the source document, will be identified and documented by each site in that site's study file. Paper documentation provided by the subject may include subject diary and Insulin Treatment Satisfaction Questionnaires to collect patient-reported outcome measures. Data from these paper documentations will be transcribed to eCRFs at the sites.

Data from complaint forms submitted to Lilly will be encoded and stored in the global product complaint management system.

### **Appendix 3.3. Study and Site Closure**

#### ***Appendix 3.3.1. Discontinuation of Study Sites***

Study site participation may be discontinued if Lilly or its designee, the investigator, or the ERB of the study site judges it necessary for medical, safety, regulatory, or other reasons consistent with applicable laws, regulations, and GCP.

#### ***Appendix 3.3.2. Discontinuation of the Study***

The study will be discontinued if Lilly or its designee, judges it necessary for medical, safety, regulatory, or other reasons consistent with applicable laws, regulations, and GCP.

**Appendix 3.4. Publication Policy**

In accordance with the sponsor's publication policy, the results of this study will be submitted for publication to a peer-reviewed journal.

---

## Appendix 4. Hepatic Monitoring Tests for Treatment-Emergent Abnormality

---

Selected tests may be obtained in the event of a treatment-emergent hepatic abnormality and may be required in follow-up with subjects in consultation with Lilly's or its designee's clinical research physician.

### Hepatic Monitoring Tests

Hepatic Hematologya	Haptoglobina
Hemoglobin	
Hematocrit	
RBC	Hepatic Coagulationa
WBC	Prothrombin time
Neutrophils, segmented	Prothrombin time, INR
Lymphocytes	
Monocytes	Hepatic Serologiesa,b
Eosinophils	Hepatitis A antibody, total
Basophils	Hepatitis A antibody, IgM
Platelets	Hepatitis B surface antigen
	Hepatitis B surface antibody
	Hepatitis B core antibody
	Hepatitis C antibody
Hepatic Chemistrya	Hepatitis E antibody, IgG
Total bilirubin	Hepatitis E antibody, IgM
Direct bilirubin	
Alkaline phosphatase	
ALT	Anti-nuclear antibodya
AST	
GGT	Alkaline Phosphatase Isoenzymesa
CPK	
	Anti-smooth muscle antibody (or anti-actin antibody)a

---

Abbreviations: ALT = alanine aminotransferase; AST = aspartate aminotransferase; CPK = creatinine phosphokinase; GGT = gamma-glutamyl transferase; Ig = immunoglobulin; INR = international normalized ratio; RBC = red blood cell; WBC = white blood cell.

a Assayed by Lilly-designated or local laboratory.

b Reflex/confirmation dependent on regulatory requirements and/or testing availability.

Note: These tests will be implemented in accordance with the most current guidance provided by the Eli Lilly Liver and Gastrointestinal Safety Advisory Committee with respect to the assessment of hepatic safety and collection of hepatic safety data.

---

## Appendix 5. Sampling Summary

---

This table summarizes the approximate number of blood samples and volumes for all sampling and tests during the study.

**Protocol ABEX Sampling Summary**

Purpose	Sample Type	Maximum Amount per Sample	Maximum Number of Samples	Maximum Total Amount
Screening tests a	Blood	4.5 mL	1	4.5 mL
Standard laboratory tests a	Blood	2 mL	1	2 mL
Total [rounded to nearest 10]		6.0 mL	-	6.0 mL
Hepatic Monitoring b	Blood	3-30 mL	-	-

a Additional samples may be drawn if needed for safety purposes.

b Based on laboratory safety values, unscheduled hepatic monitoring testing may be performed as part of subject follow-up, in consultation with Lilly-designated Medical Monitor.

---

## Appendix 6. World Health Organization Classification of Diabetes

---

**Type 2 Diabetes Mellitus:** Type 2 diabetes mellitus, although often asymptomatic, may also present with classical hyperglycemic symptoms (thirst, polyuria, and weight loss); despite hyperglycemia, ketone bodies are present in only low concentrations in the blood and urine. Coma is rare in type 2 diabetes, but may result from extreme hyperglycemia and hyperosmolarity; lactic acidosis or ketoacidosis can also occur in fulminating illness (for example, severe infection or mesenteric artery thrombosis) because of an acute increase in insulin requirements, but spontaneous ketosis does not occur. Some subjects with type 2 diabetes later progress to a state of absolute insulin deficiency.

---

**Appendix 7. Protocol Amendment I4L-IN-ABEX(b)  
Summary – A Multicenter, Open-Label, Single-Arm, Phase  
4 Study to Assess the Safety of Basaglar in Subjects with  
Type 2 Diabetes Mellitus in India**

---

## Overview

Protocol I4L-IN-ABEX – A Multicenter, Open-Label, Single-Arm, Phase 4 Study to Assess the Safety of Basaglar in Subjects with Type 2 Diabetes Mellitus in India has been amended. The new protocol is indicated by amendment (b) and will be used to conduct the study in place of any preceding version of the protocol.

The overall changes and the rationale for the changes made to this protocol are as follows:

1. The protocol title was changed from “Safety Evaluation of Basaglar in Adult Subjects with Type 2 Diabetes Mellitus in India: A Postmarketing Study” to “A Multicenter, Open-Label, Single-Arm, Phase 4 Study to Assess the Safety of Basaglar in Subjects with Type 2 Diabetes Mellitus in India” per request from Indian Ministry of Health.
2. The statistical analysis model was changed from “ANCOVA” to “general linear” model to match the statistical analysis plan.
3. Typographical errors with respect to the study identifier were corrected.

## Revised Protocol Sections

Note:	Deletions have been identified by <del>strike-throughs</del> .
	Additions have been identified by the use of underline .

### Cover Page: Protocol Title

Protocol I4L-IN-ABEX(ba)

A Multicenter, Open-Label, Single-Arm, Phase 4 Study to Assess the Safety of Basaglar in Subjects with Type 2 Diabetes Mellitus in India~~Safety Evaluation of Basaglar in Adult Subjects with Type 2 Diabetes Mellitus in India: A Postmarketing Study~~

### 1. Synopsis

#### Title of Study:

A Multicenter, Open-Label, Single-Arm, Phase 4 Study to Assess the Safety of Basaglar in Subjects with Type 2 Diabetes Mellitus in India~~Safety Evaluation of Basaglar in Adult Subjects with Type 2 Diabetes Mellitus in India: A Postmarketing Study~~

#### Summary of Study Design:

Study I4L-INMC-ABEX is a multicenter, open-label, single-arm study, that will enroll insulin-naïve subjects with T2DM. The study period consists of a screening period (Week -2 to Week 0), a treatment period (Week 0 to Week 24), and a safety follow-up visit at Week 28.

#### Statistical Analysis:

##### Statistical Methodology:

Secondary outcomes: Actual values and change in glycated hemoglobin (HbA1c) level from baseline to Week 12 and Week 24 will be analyzed in a descriptive manner on non-missing values and last observation carried forward-imputed values. Additionally, a general linear model analysis of covariance (ANCOVA) model will be performed on the full analysis set (FAS), with change from baseline in HbA1c level as the dependent variable and the baseline value of HbA1c as a covariate.

The number of hypoglycemic events per subject, the rate of hypoglycemic events per 30 days, and the rate per year, that is, the number of hypoglycemic events per subject year (365.25 days) will be assessed using a negative binomial model, with baseline HbA1c as a covariate and the log of the study treatment exposure time as an offset variable.

The analysis for other continuous secondary efficacy and safety measurements and continuous laboratory measures will use the ANCOVA~~general linear~~ model for the FAS population with the baseline value of the response variable as a covariate.

## 5.1. Overall Design

Study I4L-INMC-ABEX (ABEX) is a multicenter, open-label, single-arm, Phase 4 study to assess the safety of Basaglar in subjects with T2DM in India.

## 9.5. Subject-Reported Outcomes

If an item score is missing for a subject and  $\leq 20\%$  of the items within the domain (or overall) are missing for that subject, then the mean of the items in the domain (or overall) will be imputed for the missing item score(s). If there are  $>20\%$  missing items, the individual subject domain (or overall) score will be set to missing. Change at Week 24 from Week 4 will be analyzed using the ~~analysis of covariance (ANCOVA)~~general linear model, with the Week 4 value of the response variable as covariate.

### 10.3.2.2. Laboratory Measurements

Continuous chemistry and hematology measures will be summarized by descriptive statistics at screening visit (Week -2) and at different visits (Section 2) for the FAS population.

Continuous chemistry and hematology measures will be summarized as change from screening visit (Week -2) to Week 24 using the ~~ANCOVA~~general linear model, with the screening visit (Week -2) value of the response variable as covariate.

### 10.3.2.3. Vital Signs

Systolic blood pressure, diastolic blood pressure, and pulse rate will be summarized by descriptive statistics (mean, median, SD, SE, minimum, and maximum) by visit for the FAS population. Additionally, change from baseline to each post baseline face-to-face visit for each parameter will be summarized by means of descriptive measures as described in Section 10.3.1. Change from baseline values to Week 24 will be analyzed using the ~~ANCOVA~~general linear model, with the baseline value of the response variable as covariate after applying the LOCF method to missing values.

### 10.3.3.1. Actual and Change from Baseline HbA1c

Additionally, the change in HbA1c level from baseline to Week 24 will be analyzed using the ~~ANCOVA~~general linear model for the FAS population. The ~~ANCOVA~~general linear model will evaluate the change from baseline in HbA1c level as the dependent variable and the baseline value of HbA1c as covariate.

### 10.3.3.3. Other Efficacy Parameters

Additionally, the change from baseline to the Week 24 for 7-point SMBG levels, body mass index, and body weight will be analyzed using the ~~ANCOVA~~general linear model for the FAS population. The model will evaluate the change from baseline in HbA1c level as the dependent variable, with the baseline value of the variable as covariate, after applying the LOCF method to missing values.

#### 10.3.4. Analyses of Subject-Reported Outcomes

Subject responses to the ITSQ will be reported as overall and domain scores at Weeks 4 and 24. These scores will be summarized by descriptive statistics (mean, median, SD, SE, minimum, and maximum) by visit for the FAS population. Change at Week 24 from Week 4 will be analyzed using the ANCOVA-general linear model, with the Week 4 value of the response variable as covariate, after applying the LOCF method to missing values.

1.1 Introduction

This document describes the rules and conventions to be used in the presentation and analysis of a Phase 4, multicentre, open-label, non-randomized, single-arm study to access the Safety of Basaglar in Adult Subjects with Type 2 Diabetes Mellitus (T2DM) in India.

This statistical analysis plan (SAP), is based on protocol I4L-IN-ABEX(b), Version b, dated 04-Oct-19.

CONFIDENTIAL CS.BS.01.00 TPL-1.0: Statistical Analysis Plan Template Page 10 of 85

2. Trial objectives

The following objectives are those stated in the protocol.

2.1 Primary objectives

• To assess risk of hypoglycemia in adult subjects with T2DM in India who will be administered Basaglar.

2.2 Secondary objectives

- To assess adverse events and other safety parameters in adult subjects with T2DM in India
- To assess efficacy of Basaglar in adult subjects with T2DM in India
- To assess outcomes reported by adult subjects with T2DM in India

3. Endpoints

3.1 Primary endpoints

 Incidence of total (symptomatic or asymptomatic with FBG level of ≤54 mg/dL [≤3.0 mmol/L]) hypoglycemic events at Week 24

3.2 Secondary endpoints

- Serious adverse events (SAEs) and treatment-emergent adverse events (TEAEs)
- Rates per 30 days and per subject year of total hypoglycemic events (symptomatic or asymptomatic)
- Incidence and rates per 30 days and per subject-year of nocturnal, severe, documented symptomatic and asymptomatic hypoglycemic events
- Basal insulin dose (U/day and U/kg/day)
- Change in weight and body mass index at Week 24 from baseline
- Change in HbA1c levels at Weeks 12 and 24 from baseline
- Percentage of subjects reaching HbA1c targets ≤6.5% and <7% at week 24
- Change in FBG levels at Weeks 4, 8, and 12 from baseline
- Self-monitored 7-point SMBG levels at baseline, Weeks 4, 8, 12, and 24
- Change in 7-point SMBG levels at Weeks 4, 8, 12, and 24 from baseline
- Intrasubject variability, as measured by the standard deviation (SD) of 7-point SMBG levels
- Change in Insulin Treatment Satisfaction Questionnaire (ITSQ) score at Week
 24 from Week 4

4. Trial design

4.1 Design overview

This is a multicenter, open-label, single-arm, phase 4 study to assess the safety of Basaglar in insulin-naïve subjects with T2DM in India. The study period consists of a screening period (Week -2 to Week 0), a treatment period (Week 0 to Week 24), and a safety follow-up visit at Week 28.

Treatment period contains Week 0 to Week 12 will be the titration phase followed by the maintenance phase till Week 24. Approximately 295 subjects will be screened as per the inclusion and exclusion criteria mentioned in Sections 6.1,(in protocol) and 6.2,(in protocol) respectively, so that 250 subjects can be enrolled in the study, with a target to have a minimum of 200 subjects completing the present study. Subjects will be screened at Visit 1 and eligible subjects will be administered with Basaglar once daily (QD) from Visit 2 for a period of 24 weeks. In this study, we would seek to understand the safety of this drug in the local Indian population in accordance with the biosimilar guidelines of India. Subjects will self-administer Basaglar once daily at bedtime (starting dose will be 10 units). Subjects can self-titrate (as per outlined in table 4.1) 2-4 units once or twice in weekly until FBG levels are lowered to <100 mg/dL (5.6 mmol/L). In case of hypoglycemia, the dose can be reduced by 4 units. Subjects will continue their pre-study anti-diabetic concomitant medications.

This is a single-arm study and enrolled subjects will be treated with Basaglar using a self-titration scheme as outlined in below table 4.1.

| Fasting Blood Glucose (mg/dL) | Fasting Blood Glucose (mmol/L) | Dose Adjustments (Units) |
|-------------------------------|-----------------------------------|--------------------------|
| <80 | <4.4 | -2 |
| 80-100 | 4.4-5.6 | 0 |
| 101-130 | 5.6-7.2 | +2 |
| 131-160 | 7.3-8.9 | +4 |
| 161-190 | 8.9-10.6 | +6 |
| >190 | >10.6 | +8 |

Table 4.1

No randomization will be performed as this is a single-arm study. The sample size was calculated assuming a 15% screen failure rate, with a target to have a minimum of 200

subjects completing the study. No interim analyses and/or sample size re-estimation are planned to be performed.

4.2 Schedule of events

The schedule of evaluations and procedures to be performed at specific time points is described in the following table 4.2.

| Procedure | Screening | | | Tre | eatme | ent Pe | eriod | | Follow-up | Notes | |
|--|-----------|---|---|-----|-------|----------------|-----------------------|----|-----------|---|--|
| Visit | 1 | 2 | 3 | 4 | 5 | 6 ^a | 7 ^a | 8 | 9/ET | | |
| Week of Study | -2 | 0 | 4 | 8 | 12 | 16 | 20 | 24 | 28 | | |
| Allowable Deviation +/- (days) | | 3 | 7 | 7 | 7 | 7 | 7 | 7 | | | |
| Informed consent | X | | | | | | | | | | |
| Subject number assigned | Х | | | | | | | | | | |
| Inclusion and exclusion criteria | | | | | | | | | | | |
| Clinical Assessments | | | | | | | | | | | |
| Demography | X | | | | | | | | | | |
| Full physical examination | X | | | | | | | | | | |
| Height and weight | X | X | | | | | | X | | Height will be measured only at screening. | |
| Vital signs ^b | X | X | X | X | Х | | | X | X | SBP, DBP, and PR | |
| Medical history and family history of CV disease | X | | | | | | | | | | |
| History of substance usage | Х | X | X | X | Х | X | X | X | | Substances: drugs, alcohol, tobacco, and caffeine | |
| 12-lead ECG | X | | | | | | | | | To be recorded in a resting supine State | |
| Concomitant medication review | X | X | X | X | Х | X | X | X | X | | |
| AE/SAE/complaint handling | | X | X | X | Х | X | X | X | X | | |
| Hypoglycemic events | | X | X | X | Х | Х | X | X | X | | |
| Completion or discontinuation of investigation | | | × | | Х | X | X | X | X X | | |
| FBG ^c | | X | X | X | Х | | | | | | |
| 7-point SMBG measurement ^d | | X | × | X | X | | | X | | | |
| Laboratory Assessments | | | | | | | | | | | |

Table 4.2

CONFIDENTIAL

Page 14 of 85

CS.BS.01.00 TPL-1.0: Statistical Analysis Plan Template

| Hematology, clinical chemistry, and urinalysis tests | X | | | | X | | | X | | See Appendix 2 of protocol for details. Estimated glomerular filtration rate will be measured only in subjects with a history of severe |
|---|---------------------------|---|---|----|------|----------------|----------------|----|-------------------|--|
| Procedure | Screening | - | | Tr | eatm | ent P | ariad | | Followur | chronic kidney disease. |
| Visit | 1 | 2 | 3 | 4 | 5 | 6 ^a | 7 ^a | 8 | Follow-up 9/ET | Notes |
| Week of Study | -2 | 0 | 4 | | 12 | 16 | 20 | 24 | 28 | |
| Allowable Deviation +/- (days) | | 3 | 7 | 7 | 7 | 7 | 7 | 7 | 20 | |
| Pregnancy test (for WCBP only) | Х | X | | | | | | | | Serum pregnancy test at Visit 1 and urine pregnancy test at Visit 2 prior to being given the study drug |
| HIV, hepatitis B and C | Х | | | | | | | | | the study drug |
| HbA1c measurement | Х | X | | | Х | | | X | | |
| Subject-reported Outcomes | | | | | | | | ~ | | |
| ITSQ | | | X | | 1.00 | | | X | | |
| Ancillary Supplies/Diaries/ Study Drug | | | | | | | | | | |
| Trainings on signs/symptoms of hypo/hyperglycemia and insulin reactions | | X | X | Х | Х | X | X | Х | | This training is given at baseline and reinforced at every visit of the treatment period |
| Trainings on injection technique, use of glucometer and 7-point SMBG measurement | х | X | X | | Х | | | X | | This training is given during screening and reinforced at every face-to-face visit of the treatment period |
| Self-titration training ^e | | X | X | | X | х | х | Х | | This training is given at baseline and reinforced at every visit of the treatment period |
| Dispense study drug | | X | Х | X | Х | | | | | |
| and study diary Collect unused study | | | V | V | X | | | | | |
| drug and study diary | | | X | X | Х | | | Х | | |
| Dispense glucometer | | X | _ | - | | | | - | - | |
| Compliance to study | Contraction of the second | X | X | Y | Х | X | V | V | | |
| drug administration | | | ^ | | ^ | ^ | X | Х | | |
| Adjust insulin dose (if required) | | | X | x | X | | | X | | Site personnel will review the Basaglar dose and FBG levels recorded in the subject diary. They may recommend change in dose of Basaglar if required. |

CONFIDENTIAL CS.BS.01.00 TPL-1.0: Statistical Analysis Plan Template

Page 15 of 85

Abbreviations: AE = adverse event; CV = cardiovascular; DBP = diastolic blood pressure; ECG = electrocardiogram; ET = early termination; FBG = fasting blood glucose; HbA1c = glycated hemoglobin; HIV = human immunodeficiency virus; ITSQ = Insulin Treatment Satisfaction Questionnaire; PR = pulse rate;

SAE = serious adverse event; SBP = systolic blood pressure; SMBG = self-monitored blood glucose; WCBP = women of child-bearing potential

- a. Telephone visit.
- All vital signs should be recorded in the subject in a resting state. If there is a suspicion of postural hypotension or autonomic instability, the investigators at their discretion might decide to record the blood pressure in a supine state and then after standing for 2 minutes to detect any postural hypotension. Blood pressure measurements should be done in the left arm with sphygmomanometer held at the level of the heart. Blood pressure recording in both arms is at the investigators' discretion in selective cases of pulse volume inequality or pulse being absent in either of the arms.
- Subjects will be instructed to daily measure the FBG levels mandatorily using glucometer before the morning meal till Week 12 and record in the subject diary. Also, subjects will be instructed to measure and record the blood glucose levels using glucometer if they have symptoms of hypoglycemia (including nocturnal hypoglycemia) at any time of the day or night.
- 1. Subjects will be instructed to perform 7-point SMBG level monitoring (glucose measurements before breakfast, lunch, and dinner; 2 hours after breakfast, lunch, and dinner; and at 3 am [± 1 hour]) 2-3 days in the week prior to Visits 2, 3, 4, 5, and 8, and record the values in the subject diary. Subjects will be instructed to carry the glucometers to the sites on Visits 3, 4, 5, and 8.
- . Subjects will be instructed to record the actual time and dose of Basaglar administration in the subject diary.

5. Changes/deviations from the planned analysis

Any deviation in implementing original statistical plan will be described and justified in the final clinical study report.

6. Analysis populations

Agreement and authorization of participants included/excluded from each analysis population will be reached prior to final database hard lock. Sponsor will supply a list of all participants to be excluded from the relevant analysis populations, including the reason(s) for exclusion from the analysis populations.

6.1 Enrolled Population Set (ENRL)

This analysis population will include all participants who sign informed consent form.

"Y" for subjects who have signed ICF, Else set to "N".

6.2 Full Analysis Set (FAS) / Safety Analysis Set (SAF)

FAS and SAF are identical to each other as this is single arm trial and no randomization occurs. So, we will indicate this population as FAS for analysis purpose.

This population will include all enrolled participants who take at least 1 dose of study treatment.

 "Y" for subjects who received at least one dose of the investigational product (IMP). Else set to "N".

6.3 Per-Protocol Analysis Set (PPS)

This analysis population will include all FAS subjects, who also meet the following criteria:

- a) Have no violations of inclusion/exclusion criteria
- b) Have not discontinued from the study prior to 24 weeks
- c) Have not been off study medication for more than 14 consecutive days during the treatment period
- d) Have not received chronic (lasting longer than 14 consecutive days) systemic glucocorticoid therapy (excluding topical, intra-articular, intra-ocular, and inhaled preparations)
 - Set to 'Y' if
 1. For all FAS subjects = "Y" and

- Date of completion/discontinuation is not less than date of visit 8 (week 24)
- 3. within a subject there is no DV.DVCAT = "MAJOR"

CONFIDENTIAL CS.BS.01.00 TPL-1.0: Statistical Analysis Plan Template

Page 19 of 85

7. General considerations

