### 9.1. Efficacy and Safety Assessments

#### 9.1.1. Primary Safety Assessments

##### Hypoglycemia

Information on treatment-emergent hypoglycemic events starting from Visit 2 until the last study visit (Visit 9 or early termination [ET] visit) will be collected. Subjects will be trained about signs and symptoms of hypoglycemia. Subjects will be trained to check and record their blood glucose levels if they experience symptoms suggestive of hypoglycemia. For each hypoglycemic event, subjects should record the following data in the study diaries provided by the sponsor via the investigator:

- blood glucose levels
- associated symptoms
- treatment, and
- other pertinent information.

A hypoglycemic event is defined as any time a subject feels that he or she is experiencing a sign or symptom that is associated with hypoglycemia or has a FBG level of  $\leq 54$  mg/dL (3.0 mmol/L), even if it was not associated with signs, symptoms, or treatment consistent with current guidelines.

**Severe hypoglycemia:** An event requiring assistance of another person to actively administer carbohydrates or glucagon or taking other corrective actions. Blood glucose concentrations may not be available during an event, but neurologic recovery following the return of blood glucose to normal levels is considered sufficient evidence that the event was induced by a low blood glucose concentration.

**Nocturnal hypoglycemia:** Any total hypoglycemic event that occurs after bedtime and prior to the first meal in the morning.

**Documented symptomatic hypoglycemia:** An event during which typical symptoms of hypoglycemia are accompanied by a blood glucose level of  $\leq 54$  mg/dL ( $\leq 3.0$  mmol/L) as confirmed by blood glucose measurement.

**Asymptomatic hypoglycemia:** Any event not accompanied by typical symptoms of hypoglycemia but a measured a blood glucose level of  $\leq 54$  mg/dL ( $\leq 3.0$  mmol/L) was observed.

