### 10.2. Populations for Analyses

For purposes of analysis, the following populations are defined:

Population	Description
Enrolled	All participants who sign informed consent form
Full Analysis Set (FAS)	All enrolled participants who take at least 1 dose of study treatment
Safety	Identical to FAS, as no randomization occurs (single arm trial)
Per Protocol Set (PPS)	All FAS subjects, who also meet the following criteria: a) have no violations of inclusion/exclusion criteria b) have not discontinued from the study prior to 24 weeks c) have not been off study medication for more than 14 consecutive days during the treatment period d) have not received chronic (lasting longer than 14 consecutive days) systemic glucocorticoid therapy (excluding topical, intra-articular, intra-ocular, and inhaled preparations)

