7.6 Software

All analyses will be conducted using SAS® Version 9.4 and above.

8. Statistical considerations

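### The date condition in the SAP's per-protocol flag does not implement the exclusion of subjects who discontinue before 24 weeks

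*SAP*

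**What the plan says.** Protocol 10.2 and SAP 6.3 define the PPS by the same four criteria. Criterion (b) reads "have not discontinued from the study prior to 24 weeks" in the protocol and "Have not discontinued from the study prior to 24 weeks" in the SAP.

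SAP 6.3 then gives the rule for setting the flag to Y, in three parts: the subject is in the FAS, "Date of completion/discontinuation is not less than date of visit 8 (week 24", and no deviation for the subject is categorised MAJOR.

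Other parts of the plan that bear on this:

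- The opening of SAP section 6 has population membership agreed before hard lock, and "Sponsor will supply a list of all participants to be excluded from the relevant analysis populations".
- SAP 7.6: "All analyses will be conducted using SAS® Version 9.4 and above".
- Protocol 9.1.1 collects hypoglycaemia data "until the last study visit (Visit 9 or early termination [ET] visit) will be collected". The Schedule of Activities puts early termination in the Visit 9 column, and Protocol 5.1.1 gives withdrawals assessments like those of the follow-up visit.
- SAP 8.2 lists what is imputed. Visit dates are not on the list.
- SAP 10.1 identifies early withdrawal by an End of Study status of DISCONTINUED. The PPS flag does not use that status.

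**The concern.** The written criterion and the operational condition should select the same subjects, and on the point that matters they do not. The condition compares two dates, and one of them normally does not exist for the subjects whom criterion (b) is there to remove. The SAP gives no rule for that case.

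The protocol repeats the hypoglycaemia analyses, including the primary incidence, on the PPS. It does the same for laboratory, vital-sign, adverse-event, HbA1c, weight, SMBG and ITSQ analyses. If early leavers stay in the PPS, these repeats describe a population other than the one the protocol defines, and a reader comparing them with the FAS would not know it.

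**Working it through.** **1. What the date condition does.** Take the Visit 8 date as a subject-level date. SAP 10.1 (treatment completion) and SAP 19.1.1 (primary event window) both use it that way. One fact comes from outside the documents: in SAS a missing numeric value, including a date, ranks below any number. The example days are illustrative.

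| Subject | End of study | Visit 8 | Literal test: end date not less than Visit 8 | Criterion (b) |
|---|---|---|---|---|
| Completed | Day 196 | Day 168 | passes | keep |
| Attended Visit 8, then stopped | Day 175 | Day 168 | passes | keep |
| Dropped out | Day 60 | missing | passes | exclude |
| Dropped out | Day 130 | missing | passes | exclude |
| Missed Visit 8, attended Visit 9 | Day 196 | missing | passes | keep |

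Date errors aside, an end-of-study date cannot precede a visit that the subject attended. The test therefore excludes no one with a Visit 8 date, and read literally in SAS it excludes no one without one. Visit windowing (SAP 7.1) does not rescue it: the Visit 8 window is Day 168 ± 7, that is Days 161 to 175, so an early-termination visit on Day 60 or Day 130 is not remapped to Visit 8.

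**2. The plan's own figures (Protocol 10.1).** 200 / (1 − 0.20) = 250 enrolled, and 250 / (1 − 0.15) = 294.1, rounded up to 295 screened. Both reproduce. The documents give no expected size for the PPS.

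**3. The ceiling.** 250 × 0.20 = 50 drop-outs. If all 50 leave before Visit 8, criterion (b) allows a PPS of at most 250 − 50 = 200. The literal date test alone allows 250, so drop-outs would be at most 50 / 250 = 20% of the set.

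**4. What the other controls could remove.** Let m be the share of the 50 removed by MAJOR coding or by the sponsor's list. The documents give no value, so the full range is shown. Remaining drop-outs = 50 × (1 − m); set size = 200 + 50 × (1 − m).

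| m (assumed) | Drop-outs remaining | Set size | Share |
|---|---|---|---|
| 0 | 50 | 250 | 20.0% |
| 0.25 | 37.5 | 237.5 | 15.8% |
| 0.50 | 25 | 225 | 11.1% |
| 0.75 | 12.5 | 212.5 | 5.9% |
| 1 | 0 | 200 | 0% |

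With an assumed drop-out of 5%, 10% or 30% in place of 20%, the ceiling is about 12, 25 or 75 subjects.

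**The case against.** The flag is written in words, not code. Criterion (b) stands directly above it, and a careful programmer would see the intent. The phrase could also mean the planned Day 168 of SAP Table 7.1, in which case both drop-outs in the table fail as intended. Beyond the flag, the sponsor lists every exclusion before lock, and early leavers are easy to find because their status and reason are recorded on the End of Study form. The PPS is in any case a repeat: Protocol 10.3.1 places the safety and efficacy analyses on the FAS.

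Much of this stands, and it rules out several stronger conclusions that a reader might draw:

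- *That drop-outs will be in the PPS.* Passing the date test is not enough. The MAJOR code and the sponsor's list come on top of it, and may remove some or all of them.
- *That about 50 subjects have no Visit 8.* The 20% refers to not completing the study, which runs to Week 28. Those who leave after Visit 8 count as drop-outs but rightly meet criterion (b). Some early leavers may also carry a deviation, since non-compliance and protocol deviation are among the listed withdrawal reasons.
- *That agreement between FAS and PPS would be an artefact.* This needs the ceiling to be reached. Neither document makes such agreement a test of robustness.
- *That criteria (c) and (d) are not implemented.* The MAJOR code may well carry them, as it presumably carries (a). The documents do not say.

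The objection does not save the condition itself. The Day 168 reading is unlikely given how SAP 10.1 and 19.1.1 use the date, and if it is meant the SAP must say so. Neither document says that early discontinuation is a MAJOR deviation. SAP 10.1 lists protocol deviation as a withdrawal reason separate from adverse event, withdrawal by subject and loss to follow-up, so an ordinary drop-out is not evidently coded as one. The sponsor's list is a manual step that would have to correct a rule at odds with its own criterion.

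**Conclusion.** The point holds in this form. The date condition in SAP 6.3 does not implement criterion (b): it is always met by those who attended Visit 8, and it is undefined in words, and met under a literal SAS comparison, by those who left before it. Early leavers therefore stay in the PPS unless an undefined deviation code or a manual list takes them out.

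At the planned drop-out the leak is between 0 and at most 50 of 250 subjects. Where it falls in that range cannot be determined from the documents. The upper end assumes that every drop-out leaves before Visit 8, that none is removed by the other two controls, and that the comparison is programmed without a check for a missing date.

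The flag leaves the FAS results, including the FAS primary incidence, unchanged. The correction is still worth making before lock, because it decides who is in a set on which the primary and most other analyses are repeated.

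**What to change.** Replace the second condition in SAP 6.3 with one drawn from the End of Study form: exclude a subject whose status is DISCONTINUED and whose discontinuation date is before Week 24. Define Week 24 as the Visit 8 date if that visit was attended, and otherwise as Day 168 less the 7-day window (168 − 7 = Day 161). State which day count applies, because Table 7.1 puts Visit 2 at Day 0 while the event-day formula in SAP 7.1 makes the first dose Day 1.

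Simply requiring a non-missing Visit 8 date is tempting but wrong. It would drop a subject who missed Visit 8 and continued to Visit 9, whom criterion (b) keeps.

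In the same edit, either state that breaches of (a), (c) and (d) are coded MAJOR, or derive (c) from the exposure data and (d) from the concomitant medication data.

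The cost is a few lines of SAP text and code, with no new data collection for the date rule. The PPS may become smaller, in line with Protocol 10.2.
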